### 9.2. Protocol Deviations

Protocol deviations may be identified during visits (via source data verification, for example) or after the fact, such as the site's reply to a data query that confirms that the protocol was not followed. For this project, collection of protocol deviations will be managed in the Medidata Clinical Trial Management System (CTMS) by the Site Monitor or Central Monitor during site visits or contacts. Protocol deviations will be reviewed by the Syneos Health team and the Sponsor, classified as major or minor deviations, and a list generated of subjects with significant deviations who are to be excluded from the Per-protocol Analysis Set; this list will be finalized and approved prior to database lock.

All protocol deviations, including COVID-19 related, will be listed by subject for the Safety Set.

Major protocol deviations will be summarized by treatment arm and overall for the FAS using counts and percentages of subjects.

### 9.3. Demographic and Baseline Characteristics

Demographics and baseline characteristics will be summarized for the FAS by treatment arm and overall. The following demographic variables will be listed and summarized:

- Age in years at screening
  - <40 years; 40 to <65 years; ≥65 years

Age in years at screening will be computed using SAS code similar to the following:

`floor(YRDIF(<date of birth variable>, screen date, "AGE"))`

- Sex (Male, Female)

This document is confidential.

- Child-bearing potential (Yes, No). If child bearing potential is "No", then reason will be summarized (surgically sterile, post-menopausal, other)
- Ethnicity (Hispanic or Latino, Not Hispanic or Latino)
- Race (Asian, Black, White, American Indian or Alaska Native, Native Hawaiian or Other Pacific Islander, Other, Unknown)
- Study Eye (OD, OS)

The following baseline characteristics will be listed and summarized:

- Baseline DRSS score in the study eye (43, moderate NPDR; 47, moderately severe NPDR; 53, severe NPDR)
- Baseline DRSS score in the study eye, categorical ( $\leq 47$ ,  $\geq 53$ )
- Baseline HbA1c
  - $\leq 8\%$ ;  $> 8\%$
- Diabetes diagnosis to randomization (years)
- Baseline BCVA ETDRS letter score in the study eye
  - $\leq 55$  letters; 56 – 70 letters;  $\geq 71$  letters
- Baseline CST in the study eye
  - $\leq 300 \mu\text{m}$ ;  $> 300 \mu\text{m}$
- Number of anti-VEGF injections in the study eye prior to screening
  - 0 injections; 1 to 4 injections
- Time since diagnosis of NPDR in years at Screening in the study eye
  - Medical history terms, mapped and/or reported verbatim terms, will be examined by masked team members to identify those indicating NPDR, and the identified list will be logged in the programming specifications. The start date of earliest occurrence from amongst the identified events will be the NPDR diagnosis date and the time since diagnosis at screening will be calculated as screening date minus NPDR diagnosis date, plus 1. If the NPDR diagnosis date is missing only the day, the day will be set to 1, and if the NPDR diagnosis date is missing month and day (but not year), the month and day will be set to January 1.

Summaries will be using both categorical and continuous descriptive statistics, as detailed in [Section 8.1](#). Unless otherwise specified, percentages will be calculated based on the n in the respective population.

#### 9.4. Medical History

Medical history (inclusive of medical, surgical, and ophthalmic history) will be coded using the most recent version of Medical Dictionary for Regulatory Activities (MedDRA) version 25.0 or higher. Incidence of ocular medical history for the study eye, ocular medical history for the non-study eye, and non-ocular medical history will be separately summarized by system organ class (SOC) and preferred term (PT) for the Safety Set by treatment arm and overall. Incidence of medical conditions will be presented alphabetically by SOC and then within each SOC, alphabetically by PT for the overall column.

This document is confidential.

## **9.5. Prior and Concomitant Medications**

Medications will be coded using the most recent version of the World Health Organization Drug Dictionary (Global B3 September 2021 Version). Missing medication dates will be handled as described in [Section 8.3.1](#). Anti-VEGF medications will be identified via review of standardized medication terms and flagged in the data.

Start date and stop date for medications, in conjunction with the ongoing indicator, from the eCRF will be used to determine whether medication is prior or concomitant.

Prior medication will be defined as all medications recorded on the “Concomitant Medication” CRF taken prior to study drug administration, whether continuing or not.

Concomitant medications will be defined as medications that are ongoing at study treatment administration or started on or after study treatment administration.

The number and percentage of subjects by treatment arm and overall in the Safety Set for prior medication (ocular study-eye, ocular non-study eye, and non-ocular summarized separately) and concomitant medication (ocular study eye, ocular non-study eye, and non-ocular summarized separately) will be summarized by Anatomical Therapeutic Chemical (ATC) level 2 and PT. They will be presented by descending overall count of ATC and within each ATC, by descending overall count of PT. Subjects will be counted only once for each ATC and PT if they have multiple records of the same ATC or PT in the database.

Prior to database lock, the sponsor will conduct a masked data review of medications to determine if any are classified as prohibited medications per the protocol; prohibited medications (if any) will be flagged in the prior and concomitant medication listings.

## **9.6. Study Drug Exposure**

The number and percentage of randomized subjects who had study drug administered and who did not have study drug administered (overall and broken out by adverse event and other reason) will be summarized by treatment group and overall. The number and percentage of subjects to whom study drug was administered who had and did not have clinically significant signs/symptoms observed following injection will also be summarized by treatment group and overall.

[figure not shown]
Study drug exposure data will be presented in a data listing, including information as to whether the study drug IVT was administered, the date and time of the administration, and any clinically significant signs/symptoms observed.

This document is confidential.

## 10. Efficacy

[figure not shown]
All efficacy endpoints will be summarized descriptively by treatment arm and for EYP-1901 overall for the FAS; summarization and analyses will be repeated for the PP Set as sensitivity analyses. For continuous endpoints, n, mean, SD, median, min, and max will be presented. For categorical endpoints, numbers and percentages will be presented. The 95% confidence interval (CI) of the proportions will be constructed, as appropriate.

PPD

### 10.1. Primary Efficacy Endpoint Analysis

The primary efficacy endpoint is the percentage of subjects improving  $\geq 2$  steps from baseline in the DRSS score at Week 36 in the study eye. The percentage of subjects improving  $\geq 2$  steps from baseline in the DRSS score will be summarized descriptively using counts and percentages of subjects by randomized treatment arm at each scheduled visit (Weeks 4, 12, 24, 36, and 48) and the corresponding 95% Clopper-Pearson CI will be presented for each treatment group. PPD

#### Subgroup Analysis

The summarization and analyses (not plots) of the primary efficacy endpoint will be repeated for FAS for the following subgroups:

- Age at screening (<40 years; 40 to <65 years;  $\geq 65$  years)
- Sex (male, female)
- Baseline DRSS score in the study eye of 43 (moderate NPDR), 47 (moderately severe NPDR), and 53 (severe NPDR)
- Baseline DRSS score in the study eye, categorical ( $\leq 47$ ,  $\geq 53$ )
- Baseline BCVA ETDRS letter score in the study eye
  - $\leq$  median;  $>$  median
  - $\leq 55$  letters; 56 to 70 letters;  $\geq 71$  letters
- Baseline CST in the study eye
  - $\leq 300$  microns
  - $> 300$  microns
- Number of anti-VEGF injections in the study eye prior to screening
  - 0 injections
  - 1-4 injections
- Baseline HbA1c ( $\leq 8\%$ ;  $> 8\%$ )

This document is confidential.

- Years from NPDR diagnosis to screening
  - ≤ median; > median
  - ≤2 years; >2 to 4 years; >4 years

PPD

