4.1 Inclusion Criteria

Subjects will be considered eligible for participation in the study if all of the following inclusion criteria are satisfied:

1. Men or women ≥ 18 years of age with type 1 or 2 diabetes mellitus. Participants must have a HbA1c $\leq 12\%$ (as confirmed by laboratory assessments obtained at the Screening Visit or by a documented laboratory report dated within 60 days prior to the Screening Visit).
2. Study eye with moderately severe to severe NPDR (based on the DRSS levels 47 or 53), using standard 4-widefield digital stereoscopic fundus photographs confirmed by the CRC, in whom PRP and anti-VEGF injections can be safely deferred for at least 6 months per the Investigator.
3. Best corrected visual acuity (BCVA) using Early Treatment Diabetic Retinopathy Study (ETDRS) letter score in the study eye of ≥ 69 letters (approximate Snellen equivalent of 20/40 or better).
4. Able to understand, and willingness to sign, the informed consent and to provide access to personal health information via Health Insurance Portability and Accountability Act (HIPAA) authorization.
5. Willingness and ability to comply with all scheduled visits, restrictions, and assessments.
6. For women of childbearing potential, or men with female partners of childbearing potential, agreement to the use of an appropriate form of contraception for the duration of the study.

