**Figure 1: Study Design**

### 4.2. Subject Selection

Subjects will be enrolled in the study only if they meet all the following eligibility criteria; continued eligibility will be assessed again at treatment randomization on Day 1.

This document is confidential.

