### 8.2. Key Definitions

Baseline measurements are defined as the last non-missing measure prior to the initiation of study treatment, likely assessed at Screening or Day 1, but available unscheduled assessments will also be considered.

Study Day 1 will be the date on which study treatment is administered. Positive study days will be counted forward from Study Day 1, and negative study days will be counted backward from Study Day 1, beginning with Study Day -1. There will be no Study Day 0.

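### The fixed BCVA strata cannot separate subjects who meet the 69-letter entry limit, and the NPDR-duration formula yields days where years are meant

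*SAP*

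**What the plan says.** **BCVA.** Protocol 4.1, criterion 3, repeated in SAP 4.2.1, requires a "letter score in the study eye of ≥ 69 letters". SAP 4.2 adds that "continued eligibility will be assessed again at treatment randomization on Day 1". SAP 8.2 defines baseline as "the last non-missing measure prior to the initiation of study treatment". For the baseline table (SAP 9.3) and the primary-endpoint subgroups (SAP 10.1), the SAP uses three fixed strata: ≤55, "56 to 70 letters" and ≥71 letters. SAP 10.1 also plans a split at the median.

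**NPDR duration.** SAP 9.3 names the variable "Time since diagnosis of NPDR in years at Screening in the study eye" and then states that "time since diagnosis at screening will be calculated as screening date minus NPDR diagnosis date, plus 1". SAP 10.1 also describes it in years and uses it in two ways: a split at the median, and fixed categories of "≤2 years; >2 to 4 years; >4 years".

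**The concern.** Subgroup categories should divide the population that the trial can enrol. Two of the three BCVA strata lie wholly or mostly below the entry limit, so the fixed split would put almost everyone in one category and say little about whether response depends on baseline vision.

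For NPDR duration, the stated formula and the stated unit disagree. A programmer who coded the formula as written and applied the 2 and 4 cut-offs to the result would put subjects with recent disease in the longest-duration category. Elsewhere the SAP does write such steps out: the time-to-event formula in SAP 10.2 includes its division by 7 to reach weeks, and SAP 9.3 gives code for age in years.

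At stake are the fixed-cut panels of the subgroup table for the primary endpoint (Table 14.2.1.3, which covers every follow-up visit) and the matching rows of the baseline table.

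**Working it through.** The plan gives no figure of its own to reproduce here. The check applies its rules as written.

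**1. Eligible BCVA scores per stratum**

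Inputs: entry limit of 69 letters (Protocol 4.1); strata from SAP 9.3 and 10.1. Scores are whole letters. A scale maximum of 100 is assumed; the documents do not give one, and it affects only the last row.

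| Stratum | Scores in stratum | Scores ≥69 |
|---|---|---|
| ≤55 | 0 to 55 | none |
| 56 to 70 | 15 scores | 2 (69 and 70) |
| ≥71 | 30 scores (71 to 100) | all 30 |

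The eligible range is then 69 to 100, which is 32 scores, and 30 of the 32 fall in the top stratum. This counts scores, not subjects. The documents give no expected BCVA distribution, so the share of subjects at 69 or 70 is unknown, but the band is only two letters wide.

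Could baseline differ from the qualifying score? Criteria are rechecked on Day 1. Even if that recheck were not enforced, an eligible eye would have to lose at least 69 − 55 = 14 letters during a screening period of at most 30 days to reach ≤55. That is one letter short of the 15-letter drop that Protocol 7.1.1 counts as an ocular adverse event.

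**2. What the two-letter stratum could show**

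Arms have about 20 subjects each (SAP 4.3). Suppose the middle stratum held 1 to 3 subjects in an arm (an assumption). With no responders, the upper 95% Clopper-Pearson limit is 1 − 0.025^(1/n):

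- n = 1: interval 0 to 97.5%
- n = 2: interval 0 to 84.2%
- n = 3: interval 0 to 70.8%

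**3. NPDR duration as written**

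Formula in SAP 9.3: (screening date − diagnosis date) + 1, a count of days. Converted: that count divided by 365.25. After conversion, the cut-offs correspond to 2 × 365.25 = 730.5 days and 4 × 365.25 = 1461 days.

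| Days by formula | Category, literal | Years | Category, converted |
|---|---|---|---|
| 2 (diagnosed the day before) | ≤2 | 0.005 | ≤2 |
| 4 (3 days before) | >2 to 4 | 0.011 | ≤2 |
| 5 (4 days before) | >4 | 0.014 | ≤2 |
| 547 (1 Nov 2021 to 1 May 2023: 546 + 1) | >4 | 1.50 | ≤2 |
| 1097 | >4 | 3.00 | >2 to 4 |
| 2011 | >4 | 5.51 | >4 |

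Taken literally, every diagnosis made 4 or more days before screening falls in the top category.

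**4. What is not affected**

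Dividing every duration by the same constant leaves the ordering unchanged, so the median split forms the same groups in days or years. The BCVA median split adapts to whatever range is enrolled.

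**The case against.** **The unit is stated.** Both SAP 9.3 and 10.1 say years. The fault is one omitted division, which a programmer would probably supply, and which the masked output review (SAP 13) or program quality control (SAP 17) might catch if not. The SAP does not always spell out its conversions: time from diabetes diagnosis to randomization is listed in years with no formula, and the BCVA AUC is normalized to months with no divisor. This stands, and it makes a wrong table unlikely. It does not remove the fault: here a formula is given, it contradicts the label, and the year convention is left open.

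**An empty stratum does no harm.** SAP 16.2.5.2 has all categories displayed even when they hold nobody. The FAS is every treated subject, so someone enrolled in deviation would still need a category, and SAP 9.3 and 10.1 also list a DRSS level of 43, outside the entry levels of 47 and 53. This stands as a reason why ≤55 is only expected to be empty, not impossible. It does not give the split any power to separate eligible subjects.

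**Working alternatives exist.** Both variables have a median split in SAP 10.1, and SAP 9.3 also summarizes baseline BCVA as a continuous variable. This stands in full.

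**What a reader might infer.** One could conclude that the whole BCVA scheme lies below the entry limit, or that both subgroup analyses fail. The documents do not support either reading: the ≥71 stratum lies wholly above the limit, and only the fixed-cut versions are affected. Part of the text after the subgroup list in SAP 10.1 is redacted, so any further handling given there cannot be judged.

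**Conclusion.** Both points hold, and both are minor.

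- **BCVA:** barring entry deviations, one of the three fixed strata has no eligible score, a second has two, and the third should hold nearly all subjects. The last statement rests on the narrowness of the 69-to-70 band, not on any distribution in the documents.
- **NPDR duration:** the formula in SAP 9.3 gives days, which SAP 10.1 cuts at 2 and 4 years. Followed literally, almost every subject falls in >4. That this would actually be programmed is possible but not likely, since the label says years. A reader should not infer that a false table is the expected result.

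Nor should a reader infer damage to the trial's main result. The primary estimate and its confidence intervals by arm use neither variable. The median splits and the continuous baseline BCVA summary stand as planned; a continuous summary of NPDR duration needs the same conversion. The affected output is subgroup and baseline tabulation with about 20 subjects per arm, in a study that SAP 4.3 says is not powered for formal testing.

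**What to change.** **BCVA (SAP 9.3 and 10.1).** Delete the three-level split and keep the planned median split. If a fixed split is wanted, set its cut-offs inside the eligible range, from 69 letters upward, before unmasking.

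**NPDR duration (SAP 9.3).** State the variable as ((screening date − diagnosis date) + 1) / 365.25 years, or use the YRDIF function that the same section applies to age. If YRDIF is used, leave out the rounding down to whole years that the age code applies: a duration of 2.5 years would become 2 and move from >2 to 4 into ≤2.

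**Cost.** Two wording edits with matching changes to the table shells, and no new data. The BCVA strata would no longer match any other study that uses the current cut-offs.

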## **10.2. Secondary Efficacy Endpoint Analyses**

### Response Endpoints

The analysis and summarization performed for the primary endpoint ([Section 10.1](#)) will be repeated for the following secondary efficacy endpoints.

- Percentage of subjects improving ≥2 steps from baseline in the DRSS score in the study eye at Weeks 24 and 48.
- Percentage of subjects improving ≥2 steps from baseline in the DRSS score in the study eye at each timepoint (remaining timepoints apart from Weeks 24, 36, and 48)
- Percentage of subjects worsening ≥2 steps from baseline in the DRSS score in the study eye at each timepoint
- Percentage of subjects improving ≥3 steps from baseline in the DRSS score in the study eye at each timepoint
- Percentage of subjects worsening ≥3 steps from baseline in the DRSS score in the study eye at each timepoint
- Percentage of subjects who developed a vision-threatening complication due to diabetic retinopathy in the study eye through Week 24, through Week 36, and through Week 48.

Vision threatening complications due to diabetic retinopathy will be indicated by the presence of “Vitreous hemorrhage” or the presence of “Tractional retinal detachment” reported on the Ocular Examination – Dilated Ophthalmoscopy CRF (proliferative diabetic retinopathy [PDR] events, and “Neovascularization for the Iris” answered as “Yes” or “Neovascularization for the Angle” answered as “Yes” per the Ocular Examination - Slit Lamp Biomicroscopy CRF (anterior segment neovascularization [ASNV] events).

Summarization and analyses will be repeated for the following subgroups – baseline DRSS in the study eye of 43 (moderate NPDR), 47 (moderately severe NPDR), and 53 (severe NPDR), and baseline DRSS score in the study eye, categorical ( $\leq 47$ ,  $\geq 53$ ).

**This document is confidential.**

- Percentage of subjects who developed CI-DME in the study eye through Week 24, through Week 36, and through Week 48.

The occurrence of a CI-DME event in the study eye will be identified via examination of centrally read custom algorithm CST data and adverse events. For the CST data at any given time point, if results are available for no more than 2 raters, the average value will be used, and if results are available for three raters, the median value will be used. CI-DME will have occurred when an adverse event occurs which has a mapped preferred term of 'Cystoid macular oedema', 'Diabetic retinal oedema', or 'Macular oedema', for which the temporally closest CST measurement is greater than or equal to 320 microns.

Two additional endpoints will also be summarized.

- Macular edema (Definition 1) will have occurred when an adverse event occurs which has a mapped preferred term of 'Cystoid macular oedema', 'Diabetic retinal oedema', or 'Macular oedema'.
- Macular edema (Definition 2) will have occurred when an adverse event occurs which has a mapped preferred term of 'Cystoid macular oedema', 'Diabetic retinal oedema', or 'Macular oedema', and which has treatment with a concomitant medication with a mapped preferred term of 'aflibercept', 'ranibizumab', 'bevacizumab', or 'faricimab'.

- Percentage of subjects who received anti-VEGF or additional standard of care intervention due to ocular diabetic complications in the study eye through Week 24, through Week 36, and through Week 48.

Anti-VEGF use is identified in reported concomitant medication data as those medications with ATC code 'S01LA'.

Unique mapped concomitant medication and procedure terms and associated information will be reviewed by masked ophthalmology team members to identify those mapped concomitant medication and procedure terms that indicate the use of additional standard of care intervention due to ocular diabetic complications.

- Percentage of subjects who received PRP in the study eye, inclusive of subjects undergoing vitrectomy with endo-laser, through Week 24, through Week 36, and through Week 48.

Unique mapped procedure terms and associated information will be reviewed by masked ophthalmology team members to identify those mapped procedure terms that indicate receipt of PRP.

